### 12.5 Interim Analysis

12.4 Exploratory Analyses

There is no interim analysis planned for this study.

### 12.6 Subgroup Analyses

If applicable, for each subgroup, the HF20 sets with lower clearance specifications (KUrea = 25.5 mL/min +/- 10%) and the HF20 sets with higher clearance specifications (KUrea = 30 mL/min +/- 10%), descriptive statistics will be carried out for the reduction in BUN, creatinine and bicarbonate from baseline to 24 hours.

### 13. SAFETY AND TOLERABILITY

### 13.1 Adverse Events (AEs) and Serious Adverse Events (SAEs)

An overview of the number of patients with at least one Adverse Event (AE) (serious or non-serious), and at least one Serious Adverse Event (SAE) will be tabulated. This overview will also include the number of patients meeting each of the individual serious criteria and the number of patients related to either: study filter, device or study therapy for AEs (serious or non-serious) and SAEs as well as the number of patients with an AE (serious or non-serious) or SAE which led to a change in medication, device interruption, device withdrawal or discontinuation of the study. The overall number of AEs (serious or non-serious) will also be tabulated. The number of patients with at least one AE (serious or non-serious) and at least one SAE will be presented by MedDRA system organ class and preferred term. The number of AEs (serious or non-serious) and SAEs will be presented by MedDRA system organ class and preferred term; counts and rate of AEs or SAEs per patient treatment day will also be provided.

The number of patients with at least one AE (serious or non-serious) or SAE will be tabulated by diagnosis and severity (mild, moderate, and severe). The total number of AEs (serious or non-serious) and SAEs will also be tabulated by severity.

AEs (serious or non-serious) and SAEs will also be presented by patient and by total number of events by system organ class, preferred term and relationship to Prismaflex System, HF20 Set and study therapy.

Medication taken to treat AEs and SAEs will be tabulated by indication and brand name.

Any patient-based analysis of AEs (eg, number of patients with at least one AE) will be based on the worst severity reported for the patient for the event analyzed. If, for example, a patient reports two mild and one moderate AEs within the same system organ class and preferred term, in the patient-based analysis, the event will be presented only once under moderate severity. Prismaflex System related AEs, HF20 Set related AEs and study therapy related AEs will be considered as those AEs classified as related or possibly related with the system, filter or treatment. AEs unrelated to study system, filter or treatment will be considered those with causality assessment of not related or unlikely

related. If the relationship to the filter, system or therapy is not available or not assessable, the respective AE will be classified as system, filter or study therapy related respectively.

Data listings for AEs and SAEs will contain AE term, start date, stop date, severity, seriousness, relationship to system, relationship to filter, relationship to therapy, action taken, action taken with CRRT, and outcome.

Data listings will also be generated for AEs that caused the patient to withdraw from the study, as well as those AEs that lead to death.

Adverse events reported between signing the Informed Consent Form (ICF) and first study treatment will be listed separately.

### 13.2 Device Deficiencies/Alarms

The total number of patients who experienced a device deficiency or an alarm will be tabulated along with the total number of device deficiencies and alarms.

A summary listing of all device deficiencies and alarms will also be generated by patient.

The tabulated values will be presented for both the FAS and PPS. The listings will only be generated for the FAS.

### 13.3 Laboratory Values

Any abnormal laboratory results will be reported as adverse events if deemed clinically significant by the primary investigator. Summary tables and listings for all laboratory values at all time points will be generated and will include change from baseline values for all post baseline time points. Shift tables will also be generated to analyze any changes from baseline in low, normal or high ranged values. All lab values will be summarized as continuous values utilizing: minimum, maximum, median, mean and standard deviation along with the number of observations analyzed. All labs for all time points will also be listed by patient.

Laboratory values will be summarized and listed for the Full Analysis Set only.

### 13.4 Vital Signs

Any abnormal vital sign values will be reported as adverse events if deemed clinically significant by the primary investigator. Summary tables will be generated for all recorded time points of all vital sign parameters and will include change from baseline for post baseline time points. Shift tables will also be generated to analyze any changes

from baseline in low, normal or high vital sign values. All vital sign values will be summarized as continuous values utilizing: minimum, maximum, median, mean and standard deviation along with the number of observations analyzed. All vital signs for all time points will be listed for all patients.

Summary tables and listings for vital signs will be provided for the FAS only.

### 13.5 Fluid Overload

Calculated patient fluid overload will be summarized as a continuous variable for all time points across all patients and will also be listed by patient and time point. Fluid overload is calculated as: fluid intake (L)-fluid output (L)/ICU admission weight (kg) (×) 100%

Summary tables and listings for fluid overload will be provided for the FAS only.

### 13.6 CRRT Prescription Values

All CRRT prescription values will be listed by patient for the FAS.

### 13.7 CRRT Values

All CRRT recorded values will be summarized by minimum, maximum, median, mean and standard deviation for continuous variables or as frequency counts for categorical variables. CRRT Values will also be listed by patient and by time point.

CRRT values will be summarized for the FAS only.

### 13.8 Post Treatment Outcome Data

Post treatment outcome data will be summarized as continuous variables (except PICU outcome, dry weight attained, metabolic control attained, and death, which will be tabulated as frequencies) across all patients and will also be listed by patient. Continuous variables will be presented by minimum, maximum, median, mean and standard deviation.

Post treatment outcome data will be summarized for the FAS only.

### 13.9 Anticoagulation, HGB and Total Calcium Monitoring

Specifications for heparin anticoagulation, citrate anticoagulation, and HGB and total calcium monitoring will be listed by patient and time of use for the FAS.

### 13.10 Concomitant Medications

Any medication taken by the patient during the study will be coded to the WHO drug dictionary and will be summarized in frequency tables and patient listings.

All concomitant medication summaries will be conducted on the FAS.

### 14. OTHER RELEVANT DATA ANALYSES/SUMMARIES

Not applicable.

# 16. LIST OF TABLES, FIGURES AND LISTINGS

Table Number	Table Name	
Table 14.1.1	Subject Disposition All Subjects	
Table 14.1.2	Protocol Deviations	
Table 14.1.3	Demographic and Baseline Characteristics	
Table 14.1.4	Baseline Lab Values	
Table 14.1.5	Baseline Vital Signs	
Table 14.1.6	Treatment Compliance Full Analysis set and Per Protocol Set	
Table 14.2.1	24 Hours Percent Change from Baseline Full Analysis Set and Per Protocol Set	
Table 14.2.1.1	24 Hours Percent Change from Baseline for Sensitivity Analysis Based on Clearance Specification Subgroup Full Analysis Set and Per Protocol Set	
Table 14.2.1.3	24 Hours Percent Change from Baseline with Missing Data Imputations Ful Analysis Set	
Table 14.2.2	24 Hours Change from Baseline by Site Full Analysis Set and Per Protocol Set	
Table 14.2.2.1	24 Hours Percent Change from Baseline by Site for Sensitivity Analysis Based on Clearance Specification Subgroup Full Analysis Set and Per Protocol Set	
Table 14.2.2.3	24 Hours Percent Change from Baseline by Site with Missing Data Imputations Full Analysis Set	
Table 14.2.3	Filter Survival Time: Up to 72 hours Full Analysis Set and Per Protocol Set	
Table 14.2.4.1	Relationship between Clearance Rate and Characteristic Variables Full Analysis Set	
Table 14.2.4.2	Bicarbonate Analysis of Variance Full Analysis Set	
Table 14.3.1.1	Number of Subjects with At Least One Adverse Event (Serious and Non-Serious) Full Analysis Set	
Table 14.3.1.2	Number of Adverse Events (Serious and Non-Serious) Full Analysis Set	
Table 14.3.1.3	Number of Subjects with at Least One Adverse Event (Serious or Non-Serious) by System Organ Class and Preferred Term Full Analysis Set	
Table 14.3.1.4	Number of Subjects with at Least One Serious Adverse Event by System Organ Class and Preferred Term Full Analysis Set	
Table 14.3.1.5	1.5 Number of Adverse Events (Serious or Non-Serious) by System Organ C and Preferred Term Full Analysis Set	
Table 14.3.1.6	Number of Serious Adverse Events by System Organ Class and Preferred Term Full Analysis Set	
Table 14.3.1.7	Number of Subjects with at Least One Adverse Event (Serious or Non-Serious) by System Organ Class, Preferred Term and Severity Full Analysis	
Table 14.3.1.8	Number of Subjects with at Least One Serious Adverse Event by System Organ Class, Preferred Term and Severity Full Analysis Set	

Table 14.3.1.9	Number of Adverse Events (Serious or Non-Serious) by System Organ Class, Preferred Term and Severity Full Analysis Set
Table 14.3.1.10	Number of Serious Adverse Events by System Organ Class, Preferred Term and Severity Full Analysis Set
Table 14.3.1.11	Number of Subjects with at Least One Adverse Event (Serious or Non-Serious) Related to the Prismaflex System Full Analysis Set
Table 14.3.1.12	Number of Subjects with at Least One Serious Adverse Event Related to the Prismaflex System Full Analysis Set
Table 14.3.1.13	Number of Adverse Events (Serious or Non-Serious) Related to the Prismaflex System by System Organ Class and Preferred Term Full Analysis
Table 14.3.1.14	Number of Serious Adverse Events Related to the Prismaflex System by System Organ Class and Preferred Term Full Analysis Set
Table 14.3.1.15	Number of Subjects with Adverse Events (Serious or Non-Serious) Related to Prismaflex System by System Organ Class, Preferred Term and
Table 14.3.1.16	Number of Subjects with Serious Adverse Events Related to Prismaflex System by System Organ Class, Preferred Term and Severity Full Analysis Set
Table 14.3.1.17	Number of Subjects with at Least One Adverse Event (Serious or Non-Serious) Related to the HF20 Set Full Analysis Set
Table 14.3.1.18	Number of Subjects with at Least One Serious Adverse Event Related to the HF20 Set Full Analysis Set
Table 14.3.1.19	Number of Adverse Events (Serious or Non-Serious) Related to the HF20 Set by System Organ Class and Preferred Term Full Analysis Set
Table 14.3.1.20	Number of Serious Adverse Events Related to the HF20 Set by System Organ Class and Preferred Term Full Analysis Set
Table 14.3.1.21	Number of Subjects with Adverse Events (Serious or Non-Serious) Related to HF20 Set by System Organ Class, Preferred Term and Severity Full Analysis Set
Table 14.3.1.22	Number of Subjects with Serious Adverse Events Related to HF20 Set by System Organ Class, Preferred Term and Severity Full Analysis Set
Table 14.3.1.23	Number of Subjects with at Least One Adverse Event (Serious or Non-Serious) Related to Study Therapy Full Analysis Set
Table 14.3.1.24	Number of Subjects with at Least One Serious Adverse Event Related to Study Therapy Full Analysis Set
Table 14.3.1.25	Number of Adverse Events (Serious or Non-Serious) Related to Study Therapy Filter by System Organ Class and Preferred Term Full Analysis Set
Table 14.3.1.26	Number of Serious Adverse Events Related to the Study Therapy by System Organ Class and Preferred Term Full Analysis Set
Table 14.3.1.27	Number of Subjects with Adverse Events (Serious or Non-Serious) Related to Study Therapy by System Organ Class, Preferred Term and Severity Full Analysis Set
Table 14.3.1.28	Number of Subjects with Serious Adverse Events Related to Study Therapy by System Organ Class, Preferred Term and Severity Full Analysis Set
	· ·

Table 14.3.2	Number of Subjects Experiencing Alarms or Device Deficiencies
Table 14.3.3.1	Laboratory Summary and Change from Baseline Full Analysis Set
Table 14.3.3.2	Laboratory Shift Table Full Analysis Set
Table 14.3.4.1	Vital Signs Summary and Change from Baseline Full Analysis Set
Table 14.3.4.2	Vital Sign Shift Table Full Analysis set
Table 14.3.5	Fluid Overload Summary Full Analysis Set
Table 14.3.6	CRRT Summary Full Analysis Set
Table 14.3.7	Post Treatment Outcome Data Full Analysis Set
Table 14.3.8	Concomitant Medications Full Analysis Set
Figure Number	Figure Name
Figure 14.1.1	Subject Deposition Flow Chart All Subjects
Figure 14.2.1.1	Box Plots for Percent Change from Baseline: BUN, Creatinine, Bicarbonate Full Analysis Set
Figure 14.2.1.2	Box Plots for Percent Change from Baseline: BUN, Creatinine, Bicarbonate Per Protocol Set
Figure 14.2.2	Kaplan Meier Survival Curve Full Analysis Set and Per Protocol Set
Listing Number	Listing Name
Listing 16.2.1.1	Subject Disposition All Subjects
Listing 16.2.1.2	Inclusion Criteria All Subjects
Listing 16.2.1.3	Exclusion Criteria All Subjects
Listing 16.2.1.4	Reasons for Withdrawal All Subjects
Listing 16.2.2	Protocol Deviations All Subjects
Listing 16.2.4.1	Subject Demographics All Subjects
Listing 16.2.4.2	Subject Body Measurements at Screening All Subjects
Listing 16.2.4.3	Subject AKI History All Subjects
Listing 16.2.4.4	Concomitant Medication All Subjects
Listing 16.2.4.5	Medical History All Subjects
Listing 16.2.5.1	Subject CRRT Treatment Prescription Pt.1 All Subjects
Listing 16.2.5.2	Subject CRRT Treatment Prescription Pt.2 All Subjects
Listing 16.2.5.3	Subject CRRT Treatment Prescription Pt.3 All Subjects
Listing 16.2.5.4	Subject CRRT Values Pt. 1 All Subjects
Listing 16.2.5.5	Subject CRRT Values Pt. 2 All Subjects
Listing 16.2.5.6	Subject Filter Information All Subjects
Listing 16.2.5.6.1	Subject Filter Life All Subjects
Listing 16.2.5.7	Subject Post Treatment Outcome Data All Subjects
	·

Listing 16.2.5.8	Fluid Overload All Subjects
Listing 16.2.5.9	Heparin Anticoagulation All Subjects
Listing 16.2.5.10	Citrate Anticoagulation All Subjects
Listing 16.2.5.11	HGB/Total Calcium Monitoring
Listing 16.2.6.1	Laboratory Efficacy Response Data All Subjects
Listing 16.2.6.2	Alarms All Subjects
Listing 16.2.6.3	Device Deficiencies
Listing 16.2.7.1	Adverse Events All Subjects
Listing 16.2.7.2	Serious Adverse Events Leading to Death All Subjects
Listing 16.2.7.3	Serious Adverse Events Leading to study Withdrawal All Subjects
Listing 16.2.7.4	Adverse Events Occurring between Informed Consent and Treatment Start All Subjects
Listing 16.2.7.5	Deaths All Subjects
Listing 16.2.8.1	Laboratory Measurements All Subjects
Listing 16.2.8.2	Vital Signs All Subjects

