### 5.2 Sample Size

The sample size calculation is based on the primary objective of 24hours BUN reduction. It is anticipated that the true mean reduction at 24 hours will be some 62%, as would be obtained from a patient with initial BUN of 80 mg/dL and reaching 30 mg/dL after 24 hours of treatment. Data from the earlier M-10 study suggest that the standard deviation in the BUN reduction is about 45%.

Under these assumptions, the sample size needed to obtain 80% power is 24, as reported by SAS PROC POWER.

A target sample size of up to 30 patients is therefore proposed to allow for a possible 20% loss of data between the baseline and 24 hours mark.

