### 7. STATISTICAL ANALYSIS

### 7.1 General/Types of Analyses

Unless otherwise noted, all analyses will be performed using SAS/GRAPH® 9.4 software, SAS/STAT® 14.1 software and Base SAS® 9.4 software. Copyright© SAS Institute Inc. SAS and all other SAS Institute Inc. product or service names are registered trademarks or trademarks of SAS Institute Inc., Cary, NC, USA. All Rights Reserved.

Unless otherwise specified, treatment effects will be evaluated on the basis of a 2-sided significance level of 0.050 (when rounded to three decimal places).

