### 7.2 Handling of Missing Data

The sensitivity analyses will be performed using a multiple imputation approach. Multiple imputations using SAS PROC MI will be implemented to impute missing data under the missing at random assumption and the data sets generated will be analyzed using SAS PROC MIANALYZE.

The multiply imputed data sets are then analyzed by using standard procedures for complete data and combining the results from these analyses. Multiple imputation does not attempt to estimate each missing value through simulated values, but rather to represent a random sample of the missing values. This process results in valid statistical inferences that properly reflect the uncertainty due to missing values.

Multiple imputation inference involves three distinct phases:

- 1. The missing data are filled in m times to generate m complete data sets.
- 2. The m complete data sets are analyzed by using standard procedures.
- 3. The results from the m complete data sets are combined for the inference.

The MI procedure is a multiple imputation procedure that creates multiply imputed data sets for incomplete p-dimensional multivariate data. It uses methods that incorporate appropriate variability across the m imputations. The imputation method of choice depends on the patterns of missingness in the data and the type of the imputed variable.

Twenty (20) complete data sets based on the Markov chain Monte Carlo (MCMC) method with pre-specified covariates (age and gender) will be analyzed for the multiple imputation of the primary endpoint data as sensitivity analysis.

Three additional imputation approaches will be carried out:

- 1. Imputing the mean of the available data.
- 2. Imputing the missing values by estimating the values from a linear regression on the available data.
- 3. Imputing by worst-case approach, using the smallest observed reduction from baseline to 24 hours in BUN measurement.

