### 12. EFFICACY PARAMETERS

### 12.1 Primary Analysis

The primary analysis will be to demonstrate a mean reduction of greater than 38% in BUN at 24 hours from initiation of CRRT. This percentage of reduction is motivated by

the target of getting patients with an initial BUN of 80 mg/dL below 50 mg/dL after 24 hours of treatment.

The hypothesis to be tested is:

$$H_0$$
:  $\mu \leq 38\%$ ,

$$H_a$$
:  $\mu > 38\%$ 

Where  $\mu$  stands for the mean percentage reduction in BUN from baseline to 24 hours calculated as:

$$\mu = \frac{BUN_{0hr} - BUN_{24hr}}{BUN_{0hr}} \times 100\%$$

Where BUNohr is BUN recorded at baseline and BUN24hr is BUN recorded at 24 hours after CRRT initiation.

This hypothesis will be tested using a one-sample t test and the actual mean percentage reduction in BUN will be quantified using a 95% confidence interval.

As a supportive analysis, an analysis of variance (ANOVA) will be implemented to investigate the mean change from baseline among the different sites.

A box plot will also be generated to represent the 24 hours change in BUN from baseline.

The primary analysis of the primary endpoint will be based on the FAS. As supportive analysis, the same analysis will be carried out on the PPS.

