# 2. LIST OF TABLES, FIGURES AND LISTINGS

Table Number	Table Name
Table 14.1.1	Subject Disposition All Subjects
Table 14.1.2	Protocol Deviations
Table 14.1.3	Demographic and Baseline Characteristics
Table 14.1.4	Baseline Lab Values
Table 14.1.5	Baseline Vital Signs
Table 14.1.6	Treatment Exposure Full Analysis set / Per Protocol Set
Table 14.2.1	Laboratory Efficacy Response Percent Change from Baseline to 24 Hours Full Analysis Set / Per Protocol Set
Table 14.2.1.1	Laboratory Efficacy Response Percent Change from Baseline to 24 Hours for Sensitivity Analysis Based on Clearance Specification Subgroup Full Analysis Set / Per Protocol Set
Table 14.2.1.2	Laboratory Efficacy Response Percent Change from Baseline to 24 Hours with Missing Data Imputations Full Analysis Set
Table 14.2.2	Laboratory Efficacy Response Change from Baseline to 24 Hours (ANOVA) Full Analysis Set / Per Protocol Set
Table 14.2.2.1	Laboratory Efficacy Response Change from Baseline to 24 Hours for Sensitivity Analysis Based on Clearance Specification Subgroup (ANOVA) Full Analysis Set / Per Protocol Set
Table 14.2.2.2	Laboratory Efficacy Response Change from Baseline to 24 Hours with Missing Data Imputations (ANOVA) Full Analysis Set
Table 14.2.3	HF20 Set Filter Life Survival Analysis Full Analysis Set / Per Protocol Set
Table 14.2.3.1	HF20 Set Filter Life Cumulative Survival Rate Full Analysis Set
Table 14.2.3.2	HF20 Set Filter Life Cumulative Survival Rate Per Protocol Set
Table 14.2.4.1	Relationship Between BUN and Creatinine Clearance Rate and Characteristic Variables Full Analysis Set
Table 14.2.4.2	Bicarbonate Analysis of Variance Full Analysis Set
Table 14.3.1.1	Number of Subjects with At Least One Adverse Event (Serious and Non-Serious) Full Analysis Set
Table 14.3.1.2	Number of Adverse Events (Serious and Non-Serious) Full Analysis Set
Table 14.3.1.3	Number of Subjects with at Least One Adverse Event (Serious or Non-Serious) by System Organ Class and Preferred Term Full Analysis Set
Table 14.3.1.4	Number of Subjects with at Least One Serious Adverse Event by System Organ Class and Preferred Term Full Analysis Set
Table 14.3.1.5	Number of Adverse Events (Serious or Non-Serious) by System Organ Class and Preferred Term Full Analysis Set
Table 14.3.1.6	Number of Serious Adverse Events by System Organ Class and Preferred Term Full Analysis Set

Table Number	Table Name

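### The imputed by-site BUN table compares sites using imputations that leave site out, so that one sensitivity table can hide or invent site differences

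*SAP*

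**What the plan says.** SAP 12.1 plans, in support of the primary t test, that "an analysis of variance (ANOVA) will be implemented to investigate the mean change from baseline among the different sites". SAP 7.4 pools sites with three or fewer patients for that ANOVA.

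Both output lists contain two forms of this comparison:

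- **Table 14.2.2**, in both lists: by site, without imputation, on the FAS and PPS.
- **An imputed form**, on the FAS. In the list in SAP 16 it is Table 14.2.2.3: "24 Hours Percent Change from Baseline by Site with Missing Data Imputations Full Analysis Set". In the second list, at the end of the SAP, it appears as Table 14.2.2.2: "Laboratory Efficacy Response Change from Baseline to 24 Hours with Missing Data Imputations (ANOVA) Full Analysis Set".

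SAP 7.2 is the only place that says how values are imputed. It describes 20 data sets by the MCMC "method with pre-specified covariates (age and gender) will be analyzed for the multiple imputation of the primary endpoint data". It then adds three single-value fills: the mean of the observed values, a linear regression whose predictors are not stated, and "Imputing by worst-case approach, using the smallest observed reduction from baseline to 24 hours in BUN measurement". Site is named in none of the four. No text gives a different rule for the by-site table.

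**The concern.** An imputation model should contain the factors that the later analysis compares. Here the analysis compares sites, and the stated multiple imputation does not know which site a child came from. A missing child is filled from the all-site distribution, so a site with many losses is drawn towards the overall mean. The worst-case fill instead gives every missing child one extreme low value, so a site with many losses is pushed down whether or not it differs.

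Both site differences and site-clustered losses are plausible in this trial. Anticoagulation, priming and treatment parameters follow local practice or physician discretion (Protocol 5.6, 5.6.3.1, 5.6.5), and interruptions can lead to withdrawal (Protocol 3.2, 4.5). At stake is whether a table offered as a missing-data sensitivity analysis shows anything real about sites. Agreement with a null result could be false reassurance, and disagreement could be an artefact.

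**Working it through.** **Inputs from the documents.** SAP 5.2: up to 30 children, 20% loss, true mean reduction 62%, SD 45 points. So 30 × 0.20 = 6 values are missing and 24 observed. SAP 7.1: "treatment effects will be evaluated on the basis of a 2-sided significance level of 0.050", so the site F test is taken at 0.05. SAP 7.4: six to ten sites, small ones combined.

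**Plan's own figure.** The documents give no figure for the site ANOVA. The inputs come from the sample-size statement, so that was reproduced first. SAP 12.1 sets out to "demonstrate a mean reduction of greater than 38% in BUN", and SAP 5.2 states that "the sample size needed to obtain 80% power is 24". With a difference of 62 − 38 = 24 and SD 45, a one-sample t test at one-sided 0.05 gives N = 24 (power 81.3%), and 24 / 0.80 = 30. At two-sided 0.05 the answer is N = 30, with 70.6% power at 24. That mismatch is a separate matter.

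**Assumptions for the site check.** Five pooled sites of 6; site means evenly spaced from 32% to 92% (62 ± 30); within-site SD 45; missingness unrelated to outcome; age and gender unrelated to BUN.

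**Step 1: shrinkage.** Let f be the fraction missing at a site, m its true mean and M the value filled in. The filled site mean is (1 − f)m + fM, so its deviation from M is (1 − f)(m − M). Take M as 62; the true extreme contrast is 30 + 30 = 60.

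- Two of 6 missing at one extreme site and one of 6 at each of the others: 30 × 4/6 + 30 × 5/6 = 20 + 25 = 45.
- Three of 6 missing at both extreme sites: 30 × 3/6 + 30 × 3/6 = 30.

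The mean fill does this directly. Multiple imputation on age and gender does it on average, because its draws centre on the all-site mean.

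**Step 2: detection (simulation).** In this layout the observed-data ANOVA detects the site difference in about 26–31% of trials, and multiple imputation without site in 4–7%. Besides the shrinkage, the pooled test is over-conservative: it charges for imputation uncertainty but ignores the precision gained by borrowing across sites.

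A second layout (6 sites of 5, no true site difference, 3,000 runs per setting) shows this against a nominal 5%:

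| Method | Site effect declared |
|---|---|
| Multiple imputation, age and gender | 0.1–0.3% |
| Mean fill | 4.8–5.5% |
| Regression on age and gender (assumed predictors) | 4.5–5.7% |
| Worst case, one missing per site | 0.0% |
| Worst case, 3 + 3 missing at two sites | 35% |
| Worst case, 4 + 2 missing at two sites | 48% |

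**Step 3: worst-case fill.** With 5 sites of 6 and losses clustered at two sites, the false-positive rate is about 26%. With even losses every site moves down together and the within-site spread grows, so the test almost never rejects.

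**Step 4: site in the imputation model.** Adding site brings the false-positive rate to about 6–8% with 5 sites of 6, and to 4.2–5.1% with 6 sites of 5, where denominator degrees of freedom were capped at the complete-data value.

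**The case against.** The strongest reply is that nothing rests on this table. That is largely right.

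- A reader might infer that the plan's only site check is compromised. It is not: Table 14.2.2 gives the observed-data comparison on both analysis sets and would sit beside the imputed one.
- A reader might infer that the primary result is affected. The primary analysis is a one-sample t test that does not use site, and SAP 12.2 presents the imputations as exploring missing data in that analysis.
- A reader might say that all four fills ignore site. For the regression this is not established, because its predictors are not stated.
- Mean and regression fills do not inflate false positives in the runs above. Their harm is shrunken site means and, when losses cluster at the differing sites, lost power.
- Large site effects make the loss look dramatic but are not feasible. Site means of 62 ± 45 would reach 107%, and a BUN reduction cannot exceed 100%. Hence ± 30 is used here. At that size even the observed-data ANOVA has only about 32% power by direct calculation, and about 16% at ± 20.

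What remains is that a listed analysis, programmed as written, gives biased site contrasts and wrong error rates. Having Table 14.2.2 alongside does not tell the reader which of two conflicting tables is the artefact.

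**Conclusion.** The point holds, with low consequence. The imputed by-site table is wrong as specified: multiple imputation and the mean fill pull sites together in proportion to the loss at each site, and the worst-case fill pushes them apart when losses cluster. In the assumed layout a 60-point contrast is reported as about 45 or 30, multiple-imputation detection falls from about 26–31% to 4–7%, and the worst-case fill gives about 26% false positives under clustering.

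The directions follow from the arithmetic. The sizes depend on site layout, loss pattern and site effects that the documents do not give. Two simplifications should be stated. SD 45 is used within sites, so evenly spaced means at ± 30 give a total SD of √(45² + 450) ≈ 50, above the plan's figure. A normal model also allows individual reductions above 100%.

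The documents do not support saying that the trial lacks a valid site comparison, or that its primary conclusion is at risk. The severity is minor.

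**What to change.** Delete the imputed by-site table (Table 14.2.2.3 in SAP 16; Table 14.2.2.2 in the second list) and rely on Table 14.2.2 for the site comparison. The imputed one-sample analyses (Table 14.2.1.3; Table 14.2.1.2 in the second list) can stay.

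If the table is kept, add the pooled site factor of SAP 7.4 to the MCMC model for that table, combine site contrasts with PROC MIANALYZE, state the denominator degrees of freedom, and drop the three single-value fills from it. The drawback is imprecise site terms from 4–5 observed children per site and a type I error of about 6–8%, so deletion is cleaner.

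Either way the cost is a line in SAP 7.2 or the removal of one table, with no extra patients or data.
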